There are currently 2 randomised controlled trials (RCTs) comparing IF with arthroplasty for undisplaced FNF. Lu et al. found a slightly higher Harris Hip Score after 6 months and 1 year in favour of hemiarthroplasty but not thereafter. Dolatowski et al. found a faster mobility (TimedUp-And-Go) but no difference in the Harris Hip Score. These studies did not show a clinical difference in Harris Hip Scores, but this measure may not be the best primary outcome measure due to the ceiling effect and lack of validation for patients with hip fracture (Wamper et al.). Mobilisation on the other hand is perhaps the most important factor for mortality and should therefore be essential to measure in any hip fracture study (Kristensen et al.). There are other study types comparing IF with arthroplasty for undisplaced FNF and a meta-analysis from 2021 (Xu and Xue) with 750 patients concluded that hemiarthroplasty provided a lower implant-related complication rate, lower reoperation rate, superior hip function without increased long-term mortality. Two later studies found lower reoperation rate for IF but otherwise no difference in mortality or functional outcome (Mukka et al., Wolf et al.) and one study did not find any difference in reoperation, mortality or functional outcome (Cordero-Ampuero et al.).

Overall there is a lack of high quality studies with large sample sizes in order to compare IF with arthroplasty for undisplaced FNF.

Objectives

The aim of this trial is to compare functional outcomes of arthroplasty with internal fixation for patients over 65 years old with an undisplaced FNF. The study is designed as a national single-blinded pragmatic 1:1 RCT. The hypothesis states that arthroplasty is superior to internal fixation using the New Mobility Score (NMS) as the primary outcome after 12 months.

Section 3: Study Methods

Trial design

The SENSE trial is a national, pragmatic, single-blinded randomized controlled trial (RCT) conducted across 19 public hospitals in Denmark thereby covering app. 94% of the Danish population.

Randomization

Patients are randomly assigned in a 1:1 ratio to either receive arthroplasty or IF.

Randomization is conducted electronically through REDCap, using randomly varied blocks of sizes 4 and 6, stratified by hospital.

Sample size

The primary outcome for the study is the New Mobility Score (NMS) measured at 12 months. Based on prior studies, a clinically meaningful difference in NMS of 1 point was selected, with an expected standard deviation of 2.2 points. To achieve 95% power at a 5% significance level, 127 participants are required per group. Accounting for an anticipated 30% loss to follow-up due to mortality or other causes, the target enrolment is set at 330 participants.

Framework

This study employs a superiority framework to determine whether arthroplasty provides significantly better functional outcomes than IF. Specifically, the hypothesis is that arthroplasty will result in higher NMS scores compared to IF at 12 months post-surgery.

Interim analysis and stopping guidelines

An interim analysis will be conducted after data collection from the first 70 participants, focusing on mortality and function. If a mortality difference of 10% or an NMS difference of 2 points between groups is observed at 30 days or 3 months, respectively, the trial steering committee will review whether the trial should continue. The interim analysis did not meet the set criteria's and the steering committee recommended to continue the trial.

Timing of final analysis

The final analysis will be performed after all follow-up data, including the 12-month assessments, are collected. It is estimated that the last follow-up data is collected by February 2025. Thus, the complete analysis will be conducted in spring 2025.

Timing of outcome assessments

Assessments occur at:

Baseline:	During hospital admission with demographics, comorbidity, admission, surgery, blood samples, x-rays, NMS, Pain ratings using the Verbal Rating Scale (VRS), Oxford Hip Score (OHS), and Cumulated Ambulation Score (CAS).
2 and 6 weeks:	Pain VRS, CAS at 6 weeks
3 months:	NMS, CAS, Pain VRS, OHS, EuroQol 5-Dimension 5-Level (EQ-5D-5L), Barthel-20, and the de Morton Mobility Index (DEMMI).
6 months:	NMS, Pain VRS, OHS, EQ-5D-5L, Barthel-20, and DMMI.
12 months:	NMS (primary endpoint), Pain VRS, OHS, EQ-5D-5L, Barthel-20, DMMI, reoperation rates, and mortality.

Timeframe for collection of data

	Admission	2 weeks	6 weeks	3 months	6 months	12 months	At event
Demographics	X						
Comorbidity	X						
Admission	X						
Surgery	X						
Blood	X						
X-ray	X						X
NMS	X			X	X	X	
Pain VRS	X	X	X	X	X	X	
OHS	X			X	X	X	
EQ-5D-5L	X			X	X	X	
DEMMI	X			X	X	X	
Barthel-20	X			X	X	X	
CAS	X		X	X			
Reoperation							X
Complications							X
Mortality							X

Section 4: Statistical Principles

Confidence intervals and P values

The statistical significance level is determined to 5% (p<0.05)

No correction for multiple testing will be performed, as the study has one clearly specified main hypothesis.

The confidence intervals to be reported are 95% (95% CI)

Adherence and protocol deviations

Adherence is defined as receiving the allocated surgical procedure as per randomization. Participants will be considered adherent if they undergo the surgical procedure they were allocated to.

Adherence rates will be reported as the proportion of participants in each group who received their allocated intervention. Non-adherence, including reasons for any deviations, will be documented and categorized. Adherence to intervention will be presented as frequencies and percentages of participants adhering to intervention and participants not adhering to the intervention.

Definition of protocol deviations in the trial: Protocol deviations are defined as any deviation from the procedures described in the protocol for the study.

Description of which protocol deviations will be summarized: All deviations from protocol will be described.

Analysis population

We define the Intention-to-Treat (ITT) population includes all randomized participants analyzed according to their allocated group, regardless of the surgery performed or follow-up completion. The Per-Protocol (PP) population consists of participants who received their allocated surgical procedure without major protocol deviations. The Complete-Case population includes participants with no missing data for the primary outcome.

Section 5: Trial Population

Screening data

Screening data was not collected as part of this trial; therefore, no reporting on the representativeness of the trial sample based on screened individuals is available.

Eligibility

All patients with an undisplaced FNF classified as either Garden type I or II²¹ are evaluated. The patients are included if:

- Age ≥65 years
- Undisplaced FNF
- Posterior tilt <20°
- NMS=5 and above, indicating an ability to walk prior to the fracture
- Cognitive state intact to achieve informed consent

Patients are excluded if:

- The fracture is pathological
- The patient does not speak or understand Danish language

Recruitment

All patients are recruited in the emergency department when diagnosed with an undisplaced FNF. The admitting doctor or a senior consultant will inform the patient about the trial while the patient is in the emergency department. The information will be given verbally as well as by written participant information in an undisturbed room in the emergency department. If no next of kin are present, they will be invited to attend by phone if requested by the participant. Otherwise, an impartial assessor can be assigned. Because surgery is required to take place as quickly as possible due to a higher risk of mortality when delaying surgery, a reflection time of only 2 hours has been approved. Retrieval of informed consent will take place at either the emergency department or the ward.

Withdrawal/follow-up

Withdrawal and loss to follow-up will be recorded throughout the study. Timing and reasons will be summarized descriptively, with frequencies by treatment group. Participants with available data will remain in the ITT analysis

Baseline patient characteristics

Baseline patient characteristics include age, sex, residency, pre-fracture mobility, comorbidity (using the American Society of Anaesthesiologists Classification), diseases, medication, smoking, and alcohol.

Section 6: Analysis

Outcome definitions (primary, secondary, and other measures)

Outcome Definitions

Primary Outcome

New Mobility Score (NMS): The NMS will be assessed at baseline (pre-fracture recall), 3, 6, and 12 months, with the 12-month assessment serving as the primary endpoint. The NMS ranges from 0 to 9.

Secondary Outcomes

Oxford Hip Score (OHS): The OHS will be assessed at baseline (pre-fracture recall), 3, 6, and 12 months. Scores range from 0 to 48, with higher scores indicating better hip function.

EuroQol 5-Dimension 5-Level (EQ-5D-5L): The EQ-5D-5L measures health-related quality of life, including mobility, self-care, usual activities, pain/discomfort, and anxiety/depression, each rated from 1 to 5. A visual analog scale (VAS) from 0 to 100 (worst to best health) is also included. The EQ-5D-5L will be assessed at baseline, 3, 6, and 12 months. Scores will include an index value derived from the EQ-5D-5L scale and a VAS score ranging from 0 to 100. EQ-5D-5L scores at 12 months are a secondary outcome.

Verbal Rating Scale for Pain (VRS): The VRS for pain will measure patient-reported pain intensity on a scale from 0 (no pain) to 10 (worst possible pain). This outcome will be recorded at multiple time points to capture immediate and longer-term pain levels (2 weeks, 6 weeks, 3 months, 6 months, and 12 months). The Pain score is measured on a 0-10 scale. The VRS at 12 months is a secondary outcome.

Reoperation Rate: This outcome captures any surgical procedures related to implant failure or complications following the initial surgery. Reoperations will be tracked up to 12 months and will include any additional surgery required. This measure is categorical (yes/no), indicating whether a reoperation occurred within 12 months. Reoperations will be subdivided into major and minor: major is defined as any surgery that leads to the change of an implant or parts of it, removal of an implant (not simple removal of internal fixation), open reduction of a dislocated hip, operation due to periprosthetic fracture, or a DAIR (Debridement, antibiotics, and implant retention) procedure. Minor is defined as simple hardware removal of internal fixation or closed reduction of a dislocated hip.

Mortality: Mortality will be recorded as a binary outcome (alive/deceased) whenever the event occurs within the study period.

Exploratory Outcomes

These outcomes will not be included in the primary paper and consists for de Morton Mobility Index (DEMMI), Cumulated Ambulation Score, and X-ray measurements.

Analysis method

Primary Outcome Analysis

The primary outcome will be analyzed using a linear mixed-effects model to account for repeated measures across time points (baseline, 3, 6, and 12 months). The model will include fixed effects for time, and the

interaction between time and treatment, along with random intercepts for both hospital and individuals to account for within-subject correlation.

Time will be treated as a categorical variable.

$t = 0, \dots, T$ (observations time points) (fixed effect)

$i = 1, \dots, I$ (participants) (random effect as random intercept γ_i)

Treatment arm as fixed effect exposure with interaction with time

Baseline measurements will be included as time point 0.

Treatment effect at each time point

$$Y_{i,t} = b_{treatment,t} Treatment_i time_t + b_t time_t + \gamma_i + \varepsilon_{i,t}$$

We will use an unstructured covariance structure for the random effects. If it improves model fit, time will also be added as a random effect to account for variability in NMS across time points within individuals.

Presentation: Estimated differences in NMS scores between treatment groups will be presented with β -coefficients, 95% confidence intervals (CIs), and p-values. Treatment effects will be displayed graphically across time points to illustrate trajectories by group, with error bars representing 95% CIs.

Secondary Outcome Analyses

Oxford Hip Score (OHS), EQ-5D-5L, and Verbal Rating Scale for Pain (VRS) will each be analysed using mixed-effects models as described for the primary outcome.

Reoperation Rate and Mortality: Binary outcomes (reoperation and mortality within 12 months) will be analysed using logistic regression models with treatment as a fixed effect and hospital as a random effect. Additionally, for mortality, time-to-event analysis will be conducted using Cox proportional hazards models with baseline hazards stratified by hospital.

Presentation: For secondary outcomes, results will be presented with β -coefficients, odds ratios (for binary outcomes), hazard ratios (for time-to-event mortality analysis), 95% CIs, and p-values.

[Adjustments for Covariates](#)

Analyses of the primary and secondary outcomes will be done twice, once unadjusted, and once adjusted for following covariates: Age (continuous), Sex (male/female), Comorbidity (measured by the American Society of Anesthesiologists classification).

[Assumptions Checking for Statistical Methods](#)

Linear Mixed-Effects Models: Assumptions of normality and homoscedasticity for residuals will be checked by examining quantile-quantile (Q-Q) plots and residual-vs-fitted plots.

Logistic and Cox Models: Assumptions of linearity and proportional hazards, respectively, will be assessed. The proportional hazards assumption in Cox models will be evaluated using Schoenfeld residuals. Deviations from linearity in logistic models will be reviewed by adding polynomial terms or piecewise splines as needed.

Alternative Methods if distributional assumptions do not hold

If normality assumptions are violated in the linear mixed-effects model, non-parametric bootstrapping with 1,000 replicates will be used to estimate 95% CIs for treatment effects.

If the proportional hazards assumption is violated in the Cox regression model for mortality, we will conduct a Kaplan-Meier survival analysis. The survival curves for each treatment group will be plotted, and differences between groups will be tested using the log-rank test.

Sensitivity Analyses

Intention-to-Treat vs. Per-Protocol: The primary analysis will be conducted as intention-to-treat (ITT). A sensitivity analysis will be conducted per-protocol to assess treatment effects among participants who fully adhered to assigned interventions.

Missing Data

No missing data is expected for the Cox regression outcome (mortality and reoperation rate). For all other outcomes, mixed-effects models inherently account for missing data under the assumption that it is Missing at Random (MAR). A dropout table will be presented, summarizing the number and timing of participants lost to follow-up by treatment group.

Harms

A table summarizing all recorded harms, excluding reoperations, will be presented.

Statistical Software

All statistical analyses will be performed using Stata 18.

References

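### The enrolment target of 330 does not cover the stated 30% loss: it leaves about 231 evaluable participants against the 254 required, and about 93% power rather than 95%

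*SAP*

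**What the plan says.** The calculation is in the SAP, Section 3, Sample size. The endpoint is a single time point: "The primary outcome for the study is the New Mobility Score (NMS) measured at 12 months". The planning inputs follow: "a clinically meaningful difference in NMS of 1 point was selected", "with an expected standard deviation of 2.2 points". The required number is then given: "To achieve 95% power at a 5% significance level, 127 participants are required per group". The last step is the allowance for attrition: "Accounting for an anticipated 30% loss to follow-up due to mortality or other causes, the target enrolment is set at 330 participants".

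Allocation is equal (Section 3, Randomization), so 330 means 165 per arm. The SAP does not show how it got from 127 per group to 330, and it mentions no other allowance or rounding that would account for the figure.

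**The concern.** A number described as required for 95% power is the number that must still be available for analysis after losses. Loss to follow-up is a fraction of those enrolled, so the enrolment target is the evaluable number divided by the retained fraction. A target of 330 looks too low for 254 evaluable participants and 30% loss. It looks instead like the evaluable number multiplied by 1.3.

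What is at stake is the accuracy of the planning statement behind the trial's one confirmatory hypothesis. A reader who compares actual attrition with this paragraph would conclude that any loss up to 30% leaves the trial at its planned power. Between about 23% and 30% loss that conclusion would be wrong. For example, 12-month data on 235 participants (28.8% loss) would appear to be within plan, yet would be 254 − 235 = 19 below the number the SAP itself requires.

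**Working it through.** **Inputs, all from Section 3 of the SAP.** Difference 1 NMS point; SD 2.2; significance level 5%; power 95%; allocation 1:1; loss 30%; target enrolment 330. The SAP does not say whether the test is one- or two-sided. Two-sided is inferred, because a one-sided test gives only 105 to 106 per group.

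**Step 1. Reproduce the 127.**
- Normal approximation: n per group = 2 × (1.960 + 1.645)² × 2.2² / 1² = 125.8, so 126.
- Two-sample t-test, standardised difference 1/2.2, two-sided 5%, 95% power: n = 126.76, so 127 per group. Power at 127 is 95.04%.

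The SAP's 127 is therefore correct. It is the evaluable number, with no attrition allowance already built in. The total is 2 × 127 = 254.

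**Step 2. Reproduce the 330.**
- Dividing by the retained fraction: 254 / (1 − 0.30) = 362.9, so 363 (364 with equal arms of 182).
- Multiplying by one plus the loss: 254 × 1.30 = 330.2.

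Only the second matches 330. Because the SAP does not show the step, this origin is an inference from the match. The next step does not depend on it.

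**Step 3. What 330 delivers at 30% loss.**
- Evaluable: 330 × 0.70 = 231, or 115.5 per arm.
- Shortfall: 254 − 231 = 23 in total, 11 to 12 per arm, or about 9% of 254.
- Enrolment shortfall: 363 − 330 = 33, or about 9% of 363.

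**Step 4. Power at 115.5 per arm** (difference 1, SD 2.2, two-sided 5%).
- Normal approximation: Φ(√(115.5/2)/2.2 − 1.960) = Φ(3.454 − 1.960) = Φ(1.494) = 93.2%.
- t-test: 93.1%.
- Drop from the t-test value at 127: 95.0% − 93.1% = 1.9 points, before further rounding.

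**Step 5. The loss that 330 can absorb.** 1 − 254/330 = 0.230. Enrolling 330 keeps 254 evaluable only if loss is at most 23.0%.

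**The case against.** Nobody can reasonably dispute that 330 × 0.70 is below 254. The serious arguments concern how much it matters.

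*The effect is small.* This stands. On the SAP's own difference and SD, 90% power needs only 103 per arm, so the trial stays above 90% at the full 30% loss. Equivalently, 115.5 per arm gives 95% power for a difference of about 1.05 points instead of 1.00.

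*The primary analysis is not a two-group comparison of completers.* Section 6 specifies a mixed model on NMS at baseline, 3, 6 and 12 months. Participants without a 12-month score still contribute through their earlier scores, under a missing-at-random assumption. As an illustration, suppose earlier NMS correlates R with 12-month NMS and all 165 per arm have earlier data (neither is given in the SAP). The effective number per arm is then 1/[(1 − R²)/115.5 + R²/165]:
- R = 0.3: about 119 per arm, power 93.7%
- R = 0.5: about 125 per arm, power 94.7%
- R = 0.55: about 127 per arm, power 95.0%

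The model could therefore recover some or all of the lost power. This softens the practical effect but does not correct the statement. The sample-size section claims no such gain and gives no correlation, and its 127 reproduces as a plain comparison of two means at 12 months.

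*It is too late to matter.* The SAP is dated December 2024 and expects the last follow-up data by February 2025, so enrolment for a 12-month endpoint is in practice closed. No model, population or decision rule depends on this sentence, and the precision of the result will come from the observed data. This is a good reason to limit the remedy to wording. It is not a reason to leave the sentence as it is.

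*The 30% might mean 30% of the required number.* This does not stand. The SAP attributes the loss to mortality and other causes, which happen to enrolled participants. An allowance of 330 − 254 = 76 is 23% of those enrolled, not 30%.

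**Conclusion.** The point holds. The requirement of 127 per group is right; the step from 254 to 330 is wrong. With 330 enrolled and 30% lost, about 231 participants remain and power is about 93%, against a stated 254 and 95%. Enrolment of 330, loss of 30% and 127 evaluable per group cannot all be true.

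The conclusion rests on the SAP's own difference, SD and loss, on a two-sided 5% test (inferred because it is what gives 127), and on loss spread evenly over the arms. It takes no credit for the mixed model, in line with the SAP's own calculation. It is an error in the planning statement with a power cost of about 2 points, not evidence of a seriously underpowered trial.

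**What to change.** Leave the target at 330 and the loss assumption at 30%, and correct the last sentence of the Sample size section. For example: *The target enrolment is 330. With an anticipated 30% loss to follow-up, about 231 participants (115 to 116 per group) would be evaluable at 12 months, giving about 93% power for a difference of 1 point with an SD of 2.2 (two-sided 5%).*

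The SAP could add that 330 gives 95% power only if loss does not exceed 23%. Putting 23% in place of the 30% assumption would also make the arithmetic consistent, but it is the weaker choice because it changes a planning assumption after recruitment.

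The cost is one sentence, best changed before the analysis begins, and a stated power about 2 points lower. No extra participants are needed and the analysis does not change.

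### The covariance of the primary NMS model is not fixed: it starts from equal variance at every visit and adds random time on fit, in a form that is over-parameterised if categorical and only approximate if linear, with no fallback named

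*SAP*

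**What the plan says.** SAP Section 6, Primary Outcome Analysis, specifies a linear mixed model for NMS at baseline, 3, 6 and 12 months, with fixed effects for time and the "interaction between time and treatment, along with random intercepts for both hospital and individuals to account for within-subject correlation". The equation has one participant intercept and one residual term. Two further statements set the layout: "Time will be treated as a categorical variable", and "Baseline measurements will be included as time point 0".

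On covariance the plan says "We will use an unstructured covariance structure for the random effects", followed by "If it improves model fit, time will also be added as a random effect to account for variability in NMS". It gives no fit criterion, does not say whether random time is categorical or a linear slope, and names no fallback.

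Under Assumptions Checking: "Assumptions of normality and homoscedasticity for residuals will be checked by examining quantile-quantile (Q-Q) plots and residual-vs-fitted plots". Under Alternative Methods: "If normality assumptions are violated in the linear mixed-effects model, non-parametric bootstrapping with 1,000 replicates will be used". No remedy is attached to unequal variances, and the resampling unit is not given.

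Three other places matter. "The NMS ranges from 0 to 9" (Outcome Definitions), while Eligibility in Section 5 requires NMS of at least 5 before the fracture. The Sample size paragraph in Section 3 gives a single SD of 2.2. Secondary Outcome Analyses carries the same model over to OHS, EQ-5D-5L and VRS.

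**The concern.** A single intercept with a single residual variance gives every visit the same variance and every pair of visits the same correlation. Calling the random effects unstructured does not relax this, because a lone intercept has nothing to structure. The plan's own eligibility rule works against equal variance: baseline is an outcome row limited to 5-9, whereas follow-up can span 0-9.

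The conditional sentence is the only route to a more flexible covariance, and its form is unsettled. The categorical reading is over-parameterised and may not converge. The linear reading converges but need not reproduce the four visit variances. If neither is adopted, the equal-variance model stands. The 12-month SE, and hence the CI and p-value of the primary comparison, depends on which path is taken. At stake is the accuracy of that SE and a fully defined primary model, not the point estimate's target.

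**Working it through.** **The plan's own figure.** Difference 1, SD 2.2, two-sided 5%, power 95%: n = 2 x (1.960 + 1.645)^2 x 2.2^2 / 1^2 = 125.8, so 126 per group by the normal approximation and 127 with the t distribution. The stated 127 is reproduced. With 330 randomised (165 per arm) and complete data, the correct 12-month SE is 2.2 x sqrt(2/165) = 0.242.

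**Baseline SD.** On 5-9 the largest possible SD is (9 - 5)/2 = 2.0, with half the participants at each end. A uniform spread over the five scores gives sqrt((4+1+0+1+4)/5) = sqrt(2) = 1.41.

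**Intercept-only, by hand.** With complete data this model fits one variance, the mean of the four. For SDs 1.41/2.2/2.2/2.2: (1.99 + 3 x 4.84)/4 = 4.13, SD 2.03. Model SE over true SE is 2.03/2.2 = 0.92, so the nominal 5% test runs at 2 x Phi(-1.96 x 0.92) = about 7%.

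**Categorical random time.** An unstructured 4x4 matrix has 4 x 5/2 = 10 parameters; the residual variance makes 11. Four visits supply only 10 distinct variances and covariances, and the Jacobian has rank 10. Any residual variance from 0 to the smallest eigenvalue of the true covariance (1.14, 0.76, 2.09 and 0.96 in scenarios 1-4 below) gives the same likelihood, marginal covariance and treatment contrast.

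**Linear slope, and the procedure as a whole.** The SAP gives no SD by visit and no correlations, so these are assumed. Simulation: 165 per arm, 30% monotone dropout depending on the last observed score, REML, saturated arm-by-visit means, hospital omitted, z-test at 1.96, 3,000 replicates (Monte Carlo error about 0.4 points). The procedure adds a random slope when AIC favours it. AIC is an assumption, as the SAP names no criterion. Levels and power (1-point difference) are in %.

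| Scenario (SDs; correlation) | Level: intercept-only | Level: procedure (visit number, months) | Level: unstructured | Power: procedure / unstructured |
|---|---|---|---|---|
| 1. 1.41/2.2/2.2/2.2; exchangeable 0.5 | 7.7 | 4.3, 4.2 | 5.4 | 94.7 / 95.6 |
| 2. same SDs; autoregressive 0.7 | 8.7 | 4.5, 4.2 | 5.7 | 92.4 / 94.3 |
| 3. 2.0/2.2/2.2/2.2; exchangeable 0.5 | 5.5 | 5.2, 5.3 | 5.2 | 95.7 / 95.5 |
| 4. same SDs; autoregressive 0.7 | 7.4 | 4.5, 4.0 | 5.5 | 93.2 / 94.6 |
| 5. 1.41/2.0/2.1/2.2; exchangeable 0.5 | 9.0 | 4.5, 4.3 | 4.7 | 94.8 / 95.1 |
| 6. 1.41/2.5/2.4/2.2; exchangeable 0.5 | 6.4 | 3.9, 4.0 | 5.9 | 92.2 / 94.5 |
| 7. same SDs; autoregressive 0.7 | 6.4 | 3.0, 3.1 | 5.2 | 91.5 / 94.9 |
| 8. integer scores, bounded; latent exchangeable 0.55 | 7.0 | 3.8, 3.7 | 5.2 | 94.2 / 96.1 |
| 9. integer scores, bounded; latent autoregressive 0.75 | 7.5 | 3.9, 3.6 | 4.8 | 93.8 / 96.3 |

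Mean SE over empirical SD was 0.995-1.107 for the procedure and 0.975-1.008 for the unstructured model. The power difference runs from 0.2 points higher (scenario 3) to 94.9 - 91.5 = 3.4 points lower (scenario 7). A large-sample calculation for scenarios 1-7 agrees: SE ratio 1.00-1.12 for the slope (level 2.8-5.0%) and 0.87-0.99 for intercept-only (5.3-8.9%).

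**How general is it?** In a wider large-sample grid of 128 assumed combinations, the slope overstated the 12-month SE in 116, was exact in 4 and understated it in 8 (ratio 0.965-1.155). It is a tendency, not a rule. With a smaller baseline SD, the intercept-only level in that grid was 5.8-12.1%; the top values come from a 12-month SD of 2.5 rather than the planned 2.2.

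**The case against.** The best defence is that the reading closest to the text does no harm. Time is declared categorical, and specifying unstructured random effects makes sense only if random time is expected. That model, if it fits, gives the same contrast and SE as the fix proposed here. This stands. A reader might infer from 11 parameters for 10 elements that the treatment effect itself is undefined; it is not. What is arbitrary is the residual variance. What is missing is a rule for a failed fit.

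A reader might also infer from the intercept-only column that the primary test runs at up to 9%. The plan does not imply that. In the eight scenarios where that model exceeds 6%, AIC abandoned it for the slope in at least 99.6% of replicates. The inflated level arises only if random time is not added or cannot be fitted.

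Nor does the plan support an inference that the choice would be steered: Section 1 keeps the analyst and principal investigator blinded to allocation until the analyses are final.

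Finally, NMS is a bounded score, so the bootstrap may well be triggered, and resampling whole participants would largely correct the SE. With a participant-level sandwich SE as a stand-in, the slope model ran at 5.2% in scenarios 8-9. But the trigger is non-normality, not unequal variance, and the resampling unit is unstated, so the safeguard cannot be relied on.

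**Conclusion.** The point holds as a minor one. The primary model is not fully defined, and two of its three possible forms give a 12-month SE that tends to be wrong: too large by about 0-12% with a linear slope (level about 3-5%, power lower by at most about 3.4 points against a 95% target), or too small with the intercept alone (level about 5-9% in the scenarios above). The third, categorical form gives the right SE if it converges.

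The equal-variance assumption and the parameter count follow from the SAP's text, as does the cap of 2.0 on the baseline SD. Every other size is conditional on assumed visit SDs, correlations and dropout, on AIC as the criterion, and on leaving out the hospital intercept. The simulations do not show that the unstructured model improves the level over the slope procedure (4.7-5.9% against 3.0-5.3%). Its advantage is an accurate SE, somewhat more power in most scenarios, and a model fixed in advance.

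**What to change.** In Primary Outcome Analysis, prespecify an unstructured 4x4 residual covariance over baseline, 3, 6 and 12 months within participant, fitted by REML, with no separate participant intercept. Keep the hospital random intercept. Delete the sentence on adding random time if fit improves.

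For non-convergence, name a fallback: participant random intercept plus a separate residual variance at each visit (1 + 4 = 5 covariance parameters), with CIs from the SAP's 1,000-replicate bootstrap, resampling whole participants with all their visits. In scenarios 1-9 this fallback ran at 4.9-6.5% with its model SE and 4.8-6.0% with a participant-level sandwich SE (used in place of the bootstrap, which was not itself simulated). Its power was within 0.6 points of the unstructured model.

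Apply the same rule to OHS, EQ-5D-5L and VRS. Section 6 lists five VRS time points; the schedule in Section 3 adds one at admission. If that is used as time 0, there are six assessments and 6 x 7/2 = 21 parameters. This was estimable in simulation under assumed SDs (level 5.7%).

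The cost is two or three sentences and 10 covariance parameters for NMS instead of 2 or 4 (hospital aside), small against 330 participants. CIs will tend to be slightly narrower than with a linear slope and wider than with the intercept alone.
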